### Abbreviations

Abbreviation	Explanation
NCCN	National Comprehensive Cancer Network
NRT	Nicotine Replacement Therapy

### Revision History

Revision #	Version Date	Summary of Changes	Consent Change?
1	05.02.2023		

## Summary

Study Number: Pro2022-0894	05.02.2023
----------------------------	------------

Study Title	Quit & Fit 2.0: Feasibility and Usability Testing
Study Design	Pilot randomized controlled trial to compare tobacco cessation rates of two arms: a 6-week culturally tailored tobacco cessation intervention versus a 6-week personalized culturally-tailored tobacco cessation intervention among African American women (N=20).
Primary Objective	Examine feasibility, acceptability and satisfaction of a 6-week community-based tobacco treatment intervention.
Secondary Objective(s)	Examine self-reported stage of change for tobacco cessation.
Research Intervention(s)	community-based tobacco treatment intervention
Study Population	African American women who currently smoke tobacco in Washington, D.C. and New Jersey (Lombardi-Hackensack consortium)
Sample Size	N=20
Study Duration for individual participants	6 weeks

## 1 – Introduction

Despite lower overall smoking rates, African American women have comparable lung cancer rates to higher rate smoking groups. Smoking is the leading cause of preventable morbidity and mortality in African American women. Disparities exist in disease and death from smoking-related diseases regardless of gender. Because African American women carry a disproportionate tobacco-related disease burden, research that focuses on intervening in tobacco treatment among African American women is critical.

Tobacco treatment is the single most important preventive health behavior African American women can engage in to significantly reduce their chances of morbidity and premature mortality related to smoking-related illnesses. Although more African American men smoke compared to African American women, data show that African American women may be less successful at quitting than men. Interventions are most effective when they are paired with other lifestyle behavior interventions. Specifically, exercise has been used successfully as an adjunct to tobacco treatment interventions because exercise has the potential to reduce cigarette cravings, withdrawal symptoms and weight gain, all of which are barriers to tobacco treatment among women. Therefore, an intensive tobacco treatment program paired with a fitness component is a promising intervention to promote smoking abstinence in women who have difficulty quitting. Further, culturally tailored comprehensive interventions that address tobacco treatment among African American women are needed if we are to address the current disparities that exist in disease and death from smoking-related diseases among African American women.

## 2 – Background

### 2.1. Background/literature review (make sure you provide references)

#### **Tobacco use remains the single most preventable cause of disease and death in the United States.**

 Smoking creates well-known risks for conditions such as cancer, stroke, and heart disease. Blacks are 13% more likely to die from all types of cancer than Whites, adjusting for age. Even when controlling for differences in socioeconomic status and age, Blacks have higher all-cancer mortality across all but the highest socioeconomic decile, as compared to Whites. For lung cancer, Blacks have 2 to 3 times more risk than do any other ethnic group.

#### **Blacks face a significantly higher disease burden as a result of modifiable health behaviors as compared to their White counterparts.**

They have a higher incidence of mortality attributed to coronary heart disease, stroke, heart failure, and high blood pressure as compared to non-Hispanic Whites. The prevalence of high blood pressure (a major risk factor for coronary heart disease, stroke, heart failure, and kidney disease) is 40% higher among Blacks than in Whites, with even greater disparities seen between women. Blacks are also more likely to consume fewer servings of fruits and vegetables and have lower rates of physical activity, which are all modifiable risk factors for cancer and cardiovascular disease. Reports illustrate that Black adult females across all age groups are more likely to be overweight or obese compared to White females, and also exhibit greater disparities than between Black and White men. Consequently, Black women are in particular need of *effective targeted interventions*. Given the prevalence of smoking among women in the U.S., evidence-based tobacco treatment programs need to be translated from the research setting into community settings that are accessible to the large population of women who smoke. Women, in general, are four times more likely than men to report fear of weight gain as a reason for smoking cessation relapse and they gain significantly more weight than men who smoke following tobacco treatment. Black women are more likely to be satisfied with their body shape compared to White women; however, they report less tolerance for post-cessation weight gain and are less likely to exercise as a means of weight control.

#### **There is emerging evidence that positive changes in one's health behavior may be accompanied by other constructive health behavior changes.**

Berg et al. determined that among 539 Blacks who smoked lightly, those who reduced or quit using tobacco were more likely to walk for exercise at follow-up, after controlling for baseline walking status. Regular physical activity may be an effective means of not only promoting one's health directly but it has been associated with improved smoking cessation rates and improved mood. A recent review of 15 clinical trials demonstrated that exercise interventions combined with tobacco treatment can provide additional benefit compared to interventions that do not incorporate exercise. Commit to Quit is a smoking cessation intervention that has shown women who received cognitive-behavioral treatment (CBT) combined with an exercise intervention achieved significantly higher levels of continuous abstinence

relative to CBT plus a contact control condition. However, Commit to Quit was validated over a decade ago and advances in tobacco treatment in general have shown the importance of combined treatment and inclusion of nicotine replacement therapy (NRT) in cessation programs.

Although pilot work has attempted to translate Commit to Quit into a community setting, the studies were primarily conducted among White women and little work has been done to examine the efficacy of the approach in diverse samples. Previous research has highlighted the importance of cultural relevance in health risk communications, including tobacco interventions. Webb et al demonstrated that the culturally tailored tobacco treatment messaging produced greater culturally specific risk perceptions, readiness to quit smoking, and smoking-related knowledge. Findings support the roles of message content and culturally specific framing in the efficacy of brief written interventions for tobacco treatment in this population.

**When individuals quit smoking, they tend to gain weight.** Potential weight gain is a significant barrier to tobacco treatment; weight maintenance strategies should be included in early tobacco treatment support. Further, tobacco treatment is associated with hyperphagia and weight gain in over 70% of those individuals who attempt to quit smoking. Nicotine, which is the known main addictive component of tobacco, has anorexigenic properties and promotes body weight reductions. Thus, the idea of weight gain has acted as an incentive for the continued smoking habits and the effects of nicotine on energy homeostasis demonstrates that smoking leads to negative energy balance.

**Phone-based Interventions have the potential to drive behavior change.** Health professionals use cell phones to monitor chronic diseases, improve medication adherence, and to help individuals who smoke to quit. Telephone quit lines enhance cessation rates by over 50%. A recent cell phone cessation intervention in a low income, largely Black urban HIV clinic sample indicated that patients who received 8 phone sessions were significantly more likely at 3 months follow-up to be abstinent. A recent review concluded that text message interventions are efficacious for tobacco treatment. Recent trials are emerging that suggest mobile phones are a feasible delivery method to promote energy balance. For example, a randomized trial with 337 urban Blacks received 8 months of either weekly automated, tailored, interactive phone calls, or standard care education. The phone calls were arranged in three modules addressing hypertension medication adherence, physical activity, and diet. The intervention was associated with improvements in a measure of overall diet quality and in energy expenditure. The study suggests that diet and energy balance messages delivered by phone have promise given their convenience, scalability, and ability to deliver tailored messages for urban Blacks. Cell phones have a high penetration among underserved minority populations, and researchers have explored the use of cellular phones as a disparity-reducing advancement. Black and Hispanic groups have become the largest per capita users of basic cell phone functions. In 2014, 90% of African Americans reported cellphone ownership and 81% of all cellphone users reported sending and receiving text messages. Cellular phones do not present the digital divide -- the perceived gap between those who have access to the latest information technologies and those who

do not.

**Impact.** To date, researchers have focused on tobacco treatment interventions individually as opposed to combining positive changes in one health behavior as synergistic for another constructive health behavior change. **This application challenges the current status quo by transforming tobacco treatment in the community among Black women to address not only tobacco treatment but to proactively address the fear of weight gain with cessation using a culturally framed, targeted approach.** Ultimately, using a novel community-based tobacco treatment and exercise intervention to target community-based Black women is innovative and has the potential to engage women with individualized content that is personally relevant to foster engagement in improving their health.

## 3 – Rationale, Objectives and Hypothesis

### 3.1. Study Rationale/Problem Statement/Research question or Study significance

The rationale of the overarching study that this pilot feasibility and usability study will support is to compare the effectiveness of a 6-week community-based tobacco treatment and exercise intervention – Quit & Fit to the control (tobacco treatment intervention) targeted to African American women on tobacco cessation rates via 7-day cotinine confirmed point-prevalence abstinence (primary outcome) and secondary outcomes (caloric intake, weight changes, health beliefs).

For this study, the rationale is to pilot the feasibility, acceptability and satisfaction of the study procedures of a shortened intervention protocol that compares a culturally-tailored tobacco treatment intervention to a preference driven culturally-tailored tobacco treatment intervention.

### 3.2. Hypothesis (if applicable)

- 1) Participants will report the 6-week tobacco treatment intervention is acceptable and they are satisfied with the intervention.
- 2) Participants who complete the preference driven culturally-tailored tobacco treatment intervention will have higher rates of tobacco abstinence compared to participants in the control arm.

### 3.3. Primary Objective

**Aim 1.** Examine the feasibility, acceptability and satisfaction (primary outcome) of a 6-week community-based culturally-tailored tobacco treatment intervention to a preference driven culturally-tailored tobacco treatment intervention targeted to African American women.

**Aim 2.** Compare the effectiveness of a 6-week community-based culturally-tailored tobacco treatment intervention to a preference driven culturally-tailored tobacco treatment intervention targeted to African American women on self-reported stage of change for tobacco cessation (secondary outcome).

### 3.4. Primary Outcome Variable(s)

Feasibility, acceptability and satisfaction with the content of the educational content and the tobacco treatment intervention.

## 4 - Study Design

### 4.1 General Design

The overall study design is a 6-week community-based tobacco treatment intervention to address tobacco use in the African American female community. This pilot study is testing the feasibility, acceptability and satisfaction of a 6-week community-based culturally-tailored tobacco treatment intervention to a preference driven culturally-tailored tobacco treatment intervention targeted to African American women in New Jersey with 20 African American women; 10 participants will receive the culturally-tailored tobacco treatment intervention and 10 participants will complete the one-item Control Preference Scale and receive preference driven culturally-tailored tobacco treatment intervention based upon their control preference.

#### **4.1.1 Study Duration (if applicable)**

Total study duration = 6 months

#### **4.1.2 Number of Study Sites**

1 (HMH)

#### **4.2 Study Population**

African American women

##### **4.2.1. Number of Participants**

20

##### **4.2.2. Eligibility Criteria**

###### Inclusion Criteria:

- Self-identify as an African American woman
- Aged 18 years to 69 years
- Currently smoke 5 cigarettes per day or more
- Has smoked daily for the past one year
- Able to provide informed consent
- Generally good health as determined by medical history

###### Exclusion Criteria:

- Currently pregnant
- Diagnosis of cardiovascular disease
- Diagnosis of lung disease
- Diagnosis of mental illness
- Adults unable to consent
- Individuals who are not yet adults (infants, children, teenagers)
- Prisoners

**4.2.3. Vulnerable populations (if applicable). Vulnerable populations include children, prisoners, cognitively impaired individuals, economically or educationally disadvantaged individuals, employees, students. When vulnerable populations are**

**included, indicate what safeguards are in place to minimize coercion or undue influence to participate.**

n/a

#### **4.2.4. Withdrawal criteria (as applicable)**

n/a

#### **4.3. Study procedures**

We will recruit participants using informal recruitment through advertisements/media (e.g. advertisements, neighborhood flyers) in New Jersey.

After a participant is consented and enrolled into the study, they will complete a baseline survey, receive the home CO monitor and instructions on how to use, and be scheduled for weekly telephone calls with a certified tobacco treatment specialist (CTTS). The culturally-tailored tobacco intervention content by week via telephone call with the CTTS is listed in the table below:

Week	Tobacco Intervention Content
1	Reasons and Motivations for Quitting, Nicotine as an Addiction, Coping Response Training, Tracking Your Triggers, Education about Nicotine Replacement Therapy
2	Benefits of Quitting; Reinforce Prior Education about NRT
3	Discussion about Creating a Buddy System for Cessation and Discussion with Participant about Decreasing Daily Cigarette Use by an Additional 20% (total 40%) (CTTS will assess current cigarettes per day and ask participant to decrease cigarettes by 20% using Table 1)
4	Stress Management
5	Stress Management
6	Discussion about Environmental Influences, Stress Management, Life in your neighborhood, Gaining freedom from smoking

This intervention will address practical and logistical barriers associated with engaging patients. The intervention will integrate motivational interviewing and evidence-based tobacco treatment (i.e., cessation counseling and nicotine replacement therapy medication).

#### Intervention Content

#### **Culturally-tailored Tobacco Treatment Intervention (Arm 1) vs. Preference-Driven Culturally-tailored Tobacco Treatment Intervention (Arm 2)**

In addition to weekly cessation counseling by a CTTS for 6 weeks covering the Tobacco Intervention Content outlined above in Table 1, participants will receive weekly Content Newsletters emailed after their weekly cessation counseling session.

Participants randomized to Arm 1 will receive the Culturally-tailored Content Newsletters and participants randomized to Arm 2 will complete the one-item Control Preference Scale and receive either an Active Content Newsletter or Passive Content Newsletter. The Control Preference Scale question is:

*In terms of making decisions about your health care with your provider, which ONE of the following best describes how you would like to make these decisions?*

-  *Make the final selection about which treatment I will receive.*
-  *Make the final selection after seriously considering my provider's opinion.*
-  *Have my provider and I share responsibility for deciding what treatment is best.*
-  *Have my provider make the final decision but consider my opinion.*
-  *Leave all decisions regarding treatment to my provider.*

Individuals will be classified as follows:

1 or 2 = Active Control Preference

3 or 4 = Collaborative Control Preference

5 = Passive Control Preference

Participants will receive weekly cessation counseling by a CTTS for 6 weeks covering the Tobacco Intervention Content outlined above in Table 1. Participants will receive variations (active vs. passive control preference) of the weekly Content Newsletters emailed after their weekly cessation counseling session:

#	Active Content Newsletter	Passive Content Newsletter
1	Addresses Race and Smoking, History of Research Distrust, and Concerns about Nicotine Replacement Therapy (NRT)	Concerns about Nicotine Replacement Therapy (NRT)
2	Addresses Reasons and Motivations for Quitting, Nicotine as an Addiction, Coping Response Training, Tracking Your Triggers	Nicotine as an Addiction, Coping Response Training, Tracking Your Triggers
3	Addresses Benefits of Quitting, Stressors Unique to African Americans, Discrimination & Racism, Ways to Cope	Addresses Benefits of Quitting, Ways to Cope
4	Addresses Mood and Depression Among African Americans, Buddy System	Buddy System
5	Addresses Stress Management (same)	Addresses Stress Management (same)

Study Number: Pro2022-0894	05.02.2023
----------------------------	------------

6	Addresses Weight and African Americans, Smoking and Weight Concerns, Minimizing Weight Gain, Healthy Eating within a Soul Food Diet including Recipes	Minimizing Weight Gain
---	---	------------------------

During the Week 1 telephone call with the CTTS, the participant will be educated about combination nicotine replacement therapy over-the-counter medication and the Nicotine Replacement Therapy (NRT) patch kit + NRT lozenge kit will be mailed to the participant's home.

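### Control Preference Scale, section 4.3: answer 4 (provider has the final say) is grouped with shared decision-making in a class that has no newsletter, while its near mirror, answer 2, counts as Active

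*Combined protocol and SAP*

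**What the plan says.** Section 4.3 (Intervention Content) gives Arm 2 participants a one-item Control Preference Scale with five ordered answers, from the woman deciding alone (1) to the provider deciding everything (5). Answer 3 is the only one worded as a joint decision. Answer 2 reads "Make the final selection after seriously considering my provider's opinion" and answer 4 reads "Have my provider make the final decision but consider my opinion".

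The answers are then put into three classes: "1 or 2 = Active Control Preference", "3 or 4 = Collaborative Control Preference" and "5 = Passive Control Preference".

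Only two newsletter versions exist for Arm 2. Its participants are to "receive either an Active Content Newsletter or Passive Content Newsletter", and the same section repeats that "Participants will receive variations (active vs. passive control preference) of the weekly Content Newsletters". The content table has an Active and a Passive column, and the appendix list names an Active and a Passive set. Nothing says which version the Collaborative class receives. Section 4.1 puts 10 women in Arm 2 and says that their intervention is based on their control preference. Section 5.8.2 makes all analysis descriptive.

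**The concern.** Answers 2 and 4 are close to mirror images around answer 3. In each, one party has the final word and the other party's opinion is taken into account. The plan puts answer 2 in an end class and answer 4 in the middle class, without explanation.

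What is at stake is the content of Arm 2. Counselling topics are common to both arms, and the newsletters are where the arms are meant to differ. The Active and Passive versions differ in five of the six issues; issue 5 is marked as the same. The Passive version leaves out, among other things, the material on race and smoking, research distrust, discrimination, and mood. Where a woman is classed can therefore change the material whose acceptability and satisfaction form the primary outcome (sections 3.3 and 3.4). If the class does not follow the stated preference, the preference-driven arm is not quite what its name says.

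**Working it through.** The plan gives no figure on this point, so there is none to reproduce. The check is a reading of the five answers against the classes and the newsletters, followed by a short illustration of scale.

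**Step 1. Which criterion produces the plan's classes?** Two natural criteria can be read from the item wording.

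| Answer | Who has the final say | Does the other party have input? | Plan's class |
|---|---|---|---|
| 1 | Woman | Not stated | Active |
| 2 | Woman | Yes | Active |
| 3 | Shared | Yes | Collaborative |
| 4 | Provider | Yes | Collaborative |
| 5 | Provider | Not stated | Passive |

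Sorting by final say gives 1–2 / 3 / 4–5, that is 2, 1 and 2 answers per class. Sorting by whether both parties have input gives 1 / 2–4 / 5, that is 1, 3 and 1. The plan has 1–2 / 3–4 / 5, that is 2, 2 and 1. It follows the first criterion on the Active side and the second on the Passive side.

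**Step 2. What would each answer receive?** This depends on a rule the plan does not state, so every reading is listed, before and after moving answer 4 to Passive.

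| Newsletter for Collaborative | As now classed | With answer 4 moved | Change for answer 4 |
|---|---|---|---|
| Not stated (the text as it stands) | 1–2 Active; 3–4 none; 5 Passive | 1–2 Active; 3 none; 4–5 Passive | None assigned → Passive |
| Active | 1–4 Active; 5 Passive | 1–3 Active; 4–5 Passive | Active → Passive |
| Passive | 1–2 Active; 3–5 Passive | 1–2 Active; 3–5 Passive | No change in newsletter; class only |

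On the text as it stands, answers without a newsletter fall from 2 of 5 to 1 of 5. They reach 0 of 5 only if answer 3's newsletter is also named.

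**Step 3. Scale, on assumed frequencies.** Let p4 and p5 be the proportions giving answers 4 and 5, with n = 10 (section 4.1) and independent answers. The documents give neither proportion.

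- P(at least one answer 4) = 1 − (1 − p4)^10. At p4 = 5%: 1 − 0.95^10 = 0.40. At 10%: 1 − 0.90^10 = 0.65. At 20%: 1 − 0.80^10 = 0.89.
- P(nobody in the Passive class) as classed now = (1 − p5)^10. With answer 4 moved, it is (1 − p4 − p5)^10. Holding p4 at 10%:
  - p5 = 5%: 0.95^10 = 0.60 now, 0.85^10 = 0.20 after.
  - p5 = 10%: 0.90^10 = 0.35 now, 0.80^10 = 0.11 after.
  - p5 = 20%: 0.80^10 = 0.11 now, 0.70^10 = 0.03 after.
- Expected number in the Passive class at p4 = 10%, p5 = 5%: 10 × 0.05 = 0.5 now, 10 × 0.15 = 1.5 after.

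These figures describe how often answer 4 would occur and how large the Passive class would be. They do not say who receives which newsletter, because that depends on the missing rule in step 2.

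**The case against.** The strongest reply is that an uneven cut is not a contradiction. No section requires the classes to be symmetric. Passive could be defined as wanting no role at all; answer 5 is then the only answer that qualifies, since answer 4 keeps the woman's opinion in play. The wording is also not an exact mirror: answer 2 speaks of serious consideration, answer 4 of consideration only. The Measures appendix is listed but not reproduced, and it may give a scoring source. All of this stands. It rules out saying that the plan's own text proves the cut wrong. It does not supply the missing reason, and it does not give answer 4 a newsletter.

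A second reply concerns consequences. A reader might infer that Arm 2 already assigns newsletters by a lopsided rule, so that women who want the provider to decide are given the wrong version. The documents do not support that: there is no complete assignment rule, and if Collaborative were routed to Passive nobody's newsletter would depend on where answer 4 is classed. A reader might also take the 40% to 89% as the chance of a misclassified woman. It is the chance that someone gives answer 4, at assumed frequencies; calling her misclassified presupposes the point in dispute.

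Third, the item does not decide everything that an Arm 2 participant receives. Counselling, nicotine replacement and CO monitoring do not depend on it, and neither does newsletter 5. That is correct and limits the reach of the point. It leaves five of six newsletters in play, and these are the component that sets the arms apart.

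**Conclusion.** The point holds in a limited form. The classification is uneven and unexplained. It puts an answer that gives the provider the final word into the same class as the shared-decision answer, and that class has no newsletter. The boundary affects what is delivered under two of the three readings: the literal text, where answer 4 has no version, and routing Collaborative to Active, where answer 4 gets the version written for the opposite preference. Under the third reading only the recorded class changes.

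Filling the Collaborative gap does not by itself settle the matter, because routing that class to Active would fix the mismatch for answer 4 in place.

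The size is modest. It concerns the match of content to preference, and the fidelity and reproducibility of the intervention, in 10 women. Analysis is descriptive, so no error rate or power is involved. How many women are affected rests entirely on assumed answer frequencies. Severity is moderate. The conclusion that the cut is unexplained and leaves answer 4 without content rests on the text alone. The preference for a symmetric cut rests on reading final say as the criterion, which the plan's handling of answer 2 suggests but does not state.

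**What to change.** In section 4.3, together with the repair of the missing Collaborative newsletter:

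1. Classify 1 or 2 as Active, 3 as Collaborative, and 4 or 5 as Passive.
2. State which of the two existing newsletters the Collaborative class, now answer 3 alone, receives. Without this, answer 3 still has no content.
3. Report the raw 1 to 5 answers alongside the classes.

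If the sponsor has a sourced reason for grouping answer 4 with answer 3, the alternative is to keep the present cut, state that reason, and name the Collaborative newsletter with answer 4 explicitly in mind.

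The cost is a few lines of text, with no extra data or participants. The protocol describes no automated assignment rule; if one has been built, it must be changed to match. The one loss is that the Passive class would no longer isolate women who want no role at all. The raw answers preserve that distinction.
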